7.6.11.9 Special Situations: Abuse, Misuse, Overdose, and Medication Error

Abuse, misuse, overdose, or medication error of the study drug (as defined below) must be reported by the Investigator to the Sponsor within 24 hours using a Special Situations Report Form. If there are associated SAEs, the Investigator will also complete an SAE Form and submit to the Sponsor, within 24 hours of becoming aware.

- Abuse - Persistent or sporadic intentional excessive use of an investigational product that is accompanied by harmful physical or psychological effects.
- Misuse - Intentional and inappropriate use of an investigational product at any dose other than as directed or indicated.
- Overdose - Intentional or unintentional intake of a dose of investigational product higher than the dose assigned in the protocol.
- Medication Error - Any unintended error in the prescribing, dispensing, or administration of an investigational product. If a subject misses doses of investigational products, these not considered reportable as medication errors.

7.6.11.10 Treatment-Emergent Adverse Events

AEs reported after the initial dose of randomized study drug will be considered treatment-emergent adverse events (TEAE).

7.7 Withdrawal of Subjects from the Study or Study Drug

Subjects may voluntarily withdraw from the study for any reason at any time. A subject may be considered withdrawn if she states an intention to withdraw, fails to return for visits, or becomes lost to follow-up.

In the event of a subject's early withdrawal, the Investigator will promptly notify the Sponsor and will make every effort to determine the primary reason for the premature withdrawal from the study and will record this information on the Completion/Discontinuation eCRF. All subjects withdrawn due to AEs will be followed until resolution of any AEs or at least until the unresolved AEs are judged by the Investigator to have stabilized, becomes chronic, or the subject is lost to follow-up. During the Treatment Period, the date of last dose of study drug will be entered in the eCRF. If the subject withdrew before the end of the Treatment Period, date of discontinuation and the reason for discontinuation will be entered in the eCRF.

The following require study drug discontinuation:

- Subject develops SAE or intolerable AE considered related to study drug or if the Investigator determines the subject should be withdrawn because of safety reasons
- Subject meets Liver Discontinuation Criteria (Appendix 10)
- Subject is lost to Follow-up
- Subject has a protocol deviation that results in a significant risk to the subject's safety
- Subject is unblinded
- Subject decides to discontinue her participation in the study for any reason
- Subject is diagnosed with endometrial polyps, endometrial hyperplasia or endometrial cancer

The Investigator must register all subject discontinuations in the IxRS. In the event of a subject's withdrawal, the Investigator will promptly notify the IxRS and will make every effort to complete the end-of-study (or early termination) assessments. All patients withdrawn due to AEs will be followed until resolution or until the unresolved AEs are judged by the Investigator to have stabilized, the condition becomes chronic or the patient is lost to follow-up. All subjects who withdraw or are discontinued from the study will be followed for 14 days after the last dose. Any AEs that are ongoing 14 days after the last dose will be followed until resolution or until they are judged by the Investigator to have stabilized or the condition becomes chronic.

For subjects who are lost to follow-up (ie, those subjects whose status is unclear because they fail to appear for study visits without stating an intention to withdraw), the Investigator should show "due diligence" by documenting in the source documents steps taken to contact the subject, such as dates of telephone calls, registered letters, etc.

Subjects who have been prematurely discontinued will undergo assessments as outlined in Section 8.5. A Completion/Discontinuation form must be completed for all subjects who discontinue prematurely or who are lost to follow-up.

7.8 Appropriateness of Measurements

All efficacy and safety evaluations selected for the study are typical of those for this subject population and type of investigation, and utilize widely accepted measures.

7.9 Visit Time Window

Measurements for efficacy or safety endpoints will be performed according to the schedule as shown in Schedule of Time and Events, Table 3.1-1.

In this study, no time windows are pre-specified. All efforts should be made to ensure subjects attend the study visits according to the original visit schedule. If it is completely unavoidable, and the subject must come for a visit outside of the time outlined on the visit schedule, the site personnel must ensure that the subject has enough study drug to last until the scheduled visit. If a subject comes early or late to a study visit, the time to the next visit should be adjusted to align the future study visits with the original visit schedule. Subjects should not be exposed to study drug for more than 12 weeks.

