5.6 Packaging and Labeling

Study drug will be packaged in bottles that will be provided to the subject at Visits 2, 3, and 4. Each bottle will contain 35 tablets. Throughout the study the same size bottle will be used and will be labeled in English with a label that specifies the Sponsor, the study number, bottle identification number (BIN), number of tablets, cautionary statement, and storage conditions.

After randomization, at Visits 2, 3, and 4, each subject will receive adequate drug supply to take home; this supply will be sufficient to provide the study drug until the next clinic visit. Regardless of randomization assignment, all subjects will be required to take 1 tablet of study drug every day during the treatment period.

The Sponsor or designee will provide the Investigator with adequate quantities of the study drug. The site pharmacist or medically qualified staff member will dispense the study drug to each subject as described in Sections 5.2, 5.3 and 5.7.

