5 ANALYSIS POPULATIONS

The following populations will be used for analyses.

- **Intent-to-Treat (ITT) Population** is defined as any subject that is randomized and receives at least one dose of study medication. All efficacy analyses will be based on this population. This population will be analyzed according to the treatment to which the subject was randomized. This population will be considered primary.
- **Modified ITT (mITT) Population** will include ITT subjects who had also met the following inclusion criteria:
 - 1) The subject had 5% or fewer superficial cells in the maturation index of the vaginal smear as baseline values. (Note that subjects with no baseline value for superficial cells will not be included in the mITT Population).
 - 2) The subject had vaginal pH > 5.0 as baseline values.
 - 3) The subject had moderate or severe vaginal dryness as baseline values and selected vaginal dryness as the most bothersome VVA symptom as baseline values.

This population will be used to analyze the primary efficacy endpoints and will be considered supportive.

- **Per-Protocol Population (PP)** will consist of all subjects in the mITT population who meet all of the following:
 - 1) Complete at least 10 weeks of treatment
 - 2) Take at least 85% of the study medication within 12 weeks
 - 3) Do not have any other major protocol deviation. Major protocol deviation will be reviewed to determine eligibility for the PP Population and finalized before breaking the study blind.
 - 4) Do not have a vaginal infection or any other medical condition that would confound the primary efficacy assessment.

This population will be used to analyze the primary efficacy endpoints and will be considered supportive.

- **Safety Population** includes all randomized subjects who receive at least one dose of the study medication. This population will be analyzed according to the treatment the subjects actually received rather than the treatment to which the subjects were randomized. If a subject takes both treatments, the subject will belong to the ospemifene group.

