6.3 Study Day and Analysis Windows

Day 1 is the initial dose date for subjects. Previous day to Day 1 is expressed as Day -1, and days before Day -1 in Screening Period are expressed as Day -2, Day -3, ... , etc.

Allowance window for each of the scheduled visits is shown in Table 1.

Allowance window for diary data is shown in Table 2.

If more than one visit occurs during a visit window, the one closest to the target day will be assigned to the visit. If two visits are equidistant from the target day, the latter visit will be assigned to the visit for post-baseline values.

If a subject discontinues from the study, the data obtained at early termination visit will be treated as one visit data based on the allowance windows.

Table 1 Definition of Visit Window

Scheduled Visit	Target Day	Window (Days)
Visit 1	Day -28	≤ Day -1
Visit 2 (Day 1)	Day 1(Randomization)	Day 1
Visit 3 (Week 4)	Day 29	Day 16 to Day 43
Visit 4 (Week 8)	Day 57	Day 44 to Day 71
Visit 5 (Week 12)	Day 85	Day 72 to Day 99
Early termination	Last dosing date	+ 14

Table 2 Definition of Diary Data Window

Week	Daily Data	Weekly Data (Target Day)
Week 1	Day 1 to Day 7	Day 4 to Day 10 (Day 7)
Week 2	Day 8 to Day 14	Day 11 to Day 17 (Day 14)
Week 3	Day 15 to Day 21	Day 18 to Day 24 (Day 21)
Week 4	Day 22 to Day 28	Day 25 to Day 31 (Day 28)
Week 5	Day 29 to Day 35	Day 32 to Day 38 (Day 35)

Week	Daily Data	Weekly Data (Target Day)
Week 6	Day 36 to Day 42	Day 39 to Day 45 (Day 42)
Week 7	Day 43 to Day 49	Day 46 to Day 52 (Day 49)
Week 8	Day 50 to Day 56	Day 53 to Day 59 (Day 56)
Week 9	Day 57 to Day 63	Day 60 to Day 66 (Day 63)
Week 10	Day 64 to Day 70	Day 67 to Day 73 (Day 70)
Week 11	Day 71 to Day 77	Day 74 to Day 80 (Day 77)
Week 12	Day 78 to Day 84	Day 81 to Day 87 (Day 84)

Assessments that occur more than 14 days after the last dose of study medication will be excluded from the above visit windows.

The baseline is defined as the last value that is observed prior to the first dose of study medication. For a variable that is planned to be observed at screening and randomization, the data at randomization will be used as baseline. For such variable, if the data at randomization is missing for a subject, the data observed at screening will be used as baseline.

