8.2 Treatment Exposure and Compliance

Summary statistics of number of days of treatment exposure and treatment compliance rate will be summarized by treatment group based on electronic data capture (EDC) data.

Number of days of treatment exposure is defined as ‘actual days of correctly dosed.’
The dosing period during which a subject takes medication as follows:

$\{(\text{End date of dosing}) - (\text{initial dose date}) + 1\}$ [days]
for subjects who withdraw the study before Visit 5.

$\{(\text{Date of Visit 5}) - (\text{initial dose date}) + 1\}$ [days]
for subjects who complete the study or take medication beyond Visit 5.

Treatment compliance rate is defined as:

$100\{(\text{actual days of correctly dosed}) / (\text{duration of treatment exposure})\}$ [%].

Data until Visit 5 in ITT and Safety populations will be analyzed.

The same analysis for after Visit 5 will also be performed for Safety Population. For this analysis, subjects who continue to Part B in the previous protocol and continue taking study medication after Visit 5 will be included.

Furthermore, categorized duration of treatment exposure and treatment compliance rate will be summarized by treatment group (see Section 12 for category).

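### Protocol 7.9 does not say clearly when dosing ends if Visit 5 is late, and SAP 8.2 then understates the compliance of completers who stopped at 12 weeks

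*Protocol*

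**What the plan says.** **Protocol.** Section 7.9 sets no visit windows ("In this study, no time windows are pre-specified") and caps treatment: "Subjects should not be exposed to study drug for more than 12 weeks". For a woman who must attend off schedule, it adds that "the site personnel must ensure that the subject has enough study drug to last until the scheduled visit". Section 5.6 says of the bottles dispensed at Visits 2, 3 and 4 that "this supply will be sufficient to provide the study drug until the next clinic visit". Section 5.9 checks tablet counts against the days actually elapsed between visits.

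**SAP.** In section 6.3, "Day 1 is the initial dose date for subjects". Table 1 puts Visit 5 at a target of Day 85 with a window of Day 72 to Day 99. The same section adds: "Assessments that occur more than 14 days after the last dose of study medication will be excluded from the above visit windows".

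Section 8.2 defines the dosing period in two ways. For early withdrawals it ends on the last dosing date. It ends on the date of Visit 5 "for subjects who complete the study or take medication beyond Visit 5". The compliance rate is correctly dosed days divided by the duration of treatment exposure, times 100.

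Per-protocol criterion 2 in section 5 reads "Take at least 85% of the study medication within 12 weeks". Table 9 splits compliance at the same 85%. Section 5 makes ITT the primary population and the per-protocol set supportive.

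**The concern.** Two sites could each believe they were following the protocol when Visit 5 slips. One stops drug at Day 84 because of the cap. The other keeps the woman on drug until she attends, because supply and tablet counts are written around the visit. The SAP formula suits only the second site. At the first, the days after Day 84 enter the denominator although no dose was due, so the recorded rate is lower than the woman's true adherence.

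At stake is membership of the per-protocol set, in which the four co-primary endpoints are also analysed. If criterion 2 is computed from the 8.2 rate, the adherence needed to stay in that set rises with the lateness of Visit 5, which has nothing to do with how well the woman took her tablets.

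**Working it through.** The plan gives no compliance figure for a late attender, so there is none to reproduce.

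**Inputs**
- Cap: 12 weeks of daily dosing from Day 1, which is 84 doses, Day 1 to Day 84 (Protocol 7.9; SAP 6.3 for the day count).
- Denominator for completers: Visit 5 date minus first-dose date plus 1, which equals the Visit 5 day number *v* (SAP 8.2).
- Per-protocol cut: 85% (SAP 5).
- Latest Week 12 day: 99; at most 14 days after the last dose (SAP 6.3).

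**Assumptions**
- The denominator labelled duration of treatment exposure is the dosing period defined just above it in SAP 8.2. SAP 8.2 also describes days of exposure as correctly dosed days. If that were the denominator, every subject would score 100%, which is a separate drafting fault.
- Criterion 2 uses the 8.2 rate.
- The last dose is on Day 84.

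**Formulas**
- Highest attainable rate = 84 / *v*
- Doses needed for 85% = 0.85 × *v*, rounded up
- Missed doses tolerated = 84 − doses needed
- Days since last dose = *v* − 84

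| Visit 5 day | Highest rate | Doses needed of 84 | Adherence needed | Missed doses tolerated | Days since last dose | Week 12 value kept |
|---|---|---|---|---|---|---|
| 12-week denominator (84) | 100% | 72 (71.4 rounded up) | 85.7% | 12 | – | – |
| 85 | 98.8% | 73 (72.25) | 86.9% | 11 | 1 | yes |
| 90 | 93.3% | 77 (76.5) | 91.7% | 7 | 6 | yes |
| 92 | 91.3% | 79 (78.2) | 94.0% | 5 | 8 | yes |
| 95 | 88.4% | 81 (80.75) | 96.4% | 3 | 11 | yes |
| 98 | 85.7% | 84 (83.3) | 100% | 0 | 14 | yes |
| 99 | 84.8% | 85 (84.15), not attainable | – | – | 15 | no |

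**Example.** A woman takes 76 of 84 doses, the last on Day 84, and attends Visit 5 on Day 92. Her adherence over 12 weeks is 76/84 = 90.5%. SAP 8.2 gives 76/92 = 82.6%, below the cut. Her Week 12 value is 8 days after the last dose, so SAP 6.3 keeps it.

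**Variant.** If Day 85 is also dosed, the highest rate is 85/92 = 92.4% on Day 92 and 85/99 = 85.9% on Day 99.

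**Supply.** Supply does not settle when dosing stops. A 35-tablet bottle started at Visit 4 on Day 57 lasts through Day 91 (57 + 35 − 1), so dosing past Day 84 is physically possible.

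**The case against.** A reader might infer several stronger things, and the documents do not support them.

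- **That a fully adherent late attender is scored as non-compliant.** She is not, while her Week 12 value counts: the lowest such rate is 85.7%, on Day 98. On Day 99 she falls to 84.8%, but she is then 15 days past her last dose and SAP 6.3 already excludes the value. Only women who also missed some doses can wrongly fall below 85%.
- **That Protocol 7.9 contradicts itself outright.** The scheduled visit in the supply sentence can mean the planned date, and the next sentence realigns later visits to the planned schedule. No sentence tells a woman to dose beyond 12 weeks. The text is ambiguous, and 5.6 and 5.9 add to the ambiguity.
- **That the SAP has chosen dosing up to the visit.** The Visit 5 end point also serves women who had moved into the former Part B and were still on drug, for whom it is sensible. The category of 85 days or more in Table 9 matches a visit with target Day 85. Neither shows that the cap was set aside.
- **That late Week 12 values may be off drug without limit.** SAP 6.3 limits the gap to 14 days. A tighter limit would be a matter of preference.

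The best remaining defence is that criterion 2 says within 12 weeks and does not cite section 8.2. Read that way, the woman in the example scores 90.5% and stays in. This is a fair reading, but the SAP gives no formula for it. The 8.2 rate is the only one defined, and Table 9 splits that rate at the same 85%. The defence therefore shows that the SAP must name its denominator.

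**Conclusion.** The point holds as a minor one. Protocol 7.9, 5.6 and 5.9 leave open when dosing ends if Visit 5 is late. If dosing stops at 12 weeks, SAP 8.2 understates completers' adherence by an amount that grows with lateness: by 1.2 percentage points on Day 85 (100 − 98.8), 8.7 on Day 92 (100 − 91.3) and 14.3 on Day 98 (100 − 85.7) for a woman who took every dose. The number of missed doses tolerated at the 85% cut falls from 12 to 11, 5 and 0 on those days.

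Loss of per-protocol status follows only if criterion 2 uses the 8.2 rate and the woman missed some doses. The number of women affected cannot be computed, because the documents do not give the number of late visits, and Protocol 7.9 allows off-schedule visits only when unavoidable. Membership of the ITT set, which is primary, does not depend on compliance.

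**What to change.** 1. **Protocol or site guidance.** Reconcile 7.9, 5.6 and 5.9 so that one sentence says when dosing ends if Visit 5 is late. Which rule applies is for the sponsor to decide.
2. **SAP 8.2.** For completers, count correctly dosed days and days on which drug was due over the same interval. End it at the earlier of Visit 5 and the last day dosing was due under the reconciled rule. Both parts need the same end point: if only the denominator were cut to 84 days, a woman who dosed daily to Day 92 would score 92/84 = 109.5%.
3. **SAP 5.** State that per-protocol criterion 2 uses this rate.
4. **Optional.** List days from last dose to the Week 12 assessment for the blinded deviation review.

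The cost is a sentence in the protocol or site guidance and a few lines in the SAP, all before unblinding. No new data are needed: dosing dates and the last-dose date are already recorded (Protocol 5.3 and 7.7). The downside is that reported compliance changes slightly and a few women may move into the per-protocol set.

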8. STUDY ACTIVITIES

The overall Schedule of Time and Events for this study is provided in Table 3.1-1.

Subjects will be required to participate in both on-site clinic visits as well as a phone call that site personnel will schedule based on the subject's initial randomization date. For the scheduled phone call, subjects will be contacted by the Investigator or designee at the end of the post-study Follow-up Period. If clinically indicated and at the Investigator's discretion, the study subject may be asked to complete an unscheduled visit.

In the sections below, activities to be performed have been listed in the order that appears to simplify the process for the site and the subject. At Screening and Randomization visits, procedures that may exclude a subject immediately are to be conducted earlier to ensure subjects that will not qualify do not undergo the most invasive/uncomfortable procedures.

8.1 Screening, Visit 1 (Up to 4 Weeks Prior to Randomization)

Screening should take place up to 4 weeks (28 days) prior to randomization. Enough time between Visit 1 and Visit 2 should be allowed to receive the results of tests conducted as part of Visit 1, therefore, Visit 2 should not take place earlier than 1 week after Visit 1. The Investigator will inform each prospective subject of the nature of the study, explain the potential risks, and obtain written informed consent from the subject prior to performing any study-related procedures and prior to the administration of the study drug.

- Sign ICF
- Contact IxRS to obtain subject ID number
- Obtain urine sample for urinalysis (dipstick + central laboratory) and perform dipstick assessment prior to the next procedure
- Record demographics
- Record medical history
- Record prior therapy
- Assess inclusion and exclusion criteria
- Assessment of VVA symptoms
- Measure vital signs (BP, pulse rate, and oral temperature performed after subject is in seated or in a recumbent position ≥ 3 minutes) including height and weight
- Perform physical examination
- Perform breast examination
- Perform gynecological examination
- Measure vaginal pH
- Obtain vaginal smear for assessment of maturation index
- Obtain sample for cervical PAP smear

- Perform TVU and measure endometrial thickness
- Perform endometrial biopsy
- Obtain 12-lead ECG (performed in a supine position after ≥ 5 minutes)
- Obtain blood samples for safety laboratory tests and FSH to confirm postmenopausal status in women ≥ 45 years old who do not remember the date of the last spontaneous menstrual period OR women who had a hysterectomy without oophorectomy.
- Assess for AEs (with a start time after signing ICF)
- Conduct/order mammogram
For subjects who have a normal mammogram within 9 months prior to screening for which the results are available, those results can be used and a new mammogram is not required for eligibility assessment.

At the time of Screening, a one-time follow-up blood draw is allowed for the retest of abnormal values that may exclude the subject from study participation.

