7.5.11.2 Vaginal Infection

At all visits the sequence of procedures should follow Section 8. However, if a vaginal infection requiring medication (e.g. candida vaginitis) is identified at Visit 1 (screening) or at Visit 2 prior to randomization, the infection must be treated to resolution. After the vaginal infection is treated, 2 weeks (14 days) should be allowed to restore the local environment before continuing the screening or randomization procedures. The time necessary to treat the infection will not count against the 4-week duration of the screening period. If a vaginal infection is identified please follow these procedures:

1. If the vaginal infection is discovered during the gynecological examination (Visit 1 or Visit 2), the vaginal pH, the vaginal smear for maturation index, and the sample for cervical PAP, along with the rest of the remaining assessments for that visit, should not be conducted until the resolution of the infection is confirmed. The VVA questionnaire needs to be repeated as it should have been conducted before the gynecological examination.
2. If the infection is identified based on the results of cervical pap or vaginal smear for maturation index obtained at Visit 1, the infection should be treated until resolution. The patient should then return for an Unscheduled Visit (prior to Visit 2) for a repeat of the VVA questionnaire, gynecological examination, vaginal pH, vaginal smear (maturation index), and cervical pap, to confirm eligibility. If eligible based on these results the subject may continue to Visit 2.
3. If the infection takes longer than 30 days to treat, safety laboratory tests (hematology and chemistry) should be repeated at an Unscheduled Visit at the infection-free timepoint to confirm eligibility. If eligible based on these results the subject may continue to Visit 2 if the infection was diagnosed prior to Visit 2 or continue with the outstanding procedures from Visit 2 if the infection was diagnosed at Visit 2.
4. In the situations described in items 2 and 3 above, results of tests repeated between Visit 1 and Visit 2, at the infection-free timepoint, will be used to confirm eligibility (Visit 1) as well as baseline values (Visit 2) and do not need to be repeated again at Visit 2. The TVU, endometrial biopsy, and ECG do not need to be repeated even if they were assessed prior to the discovery of the infection.

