7.6.4 Transvaginal Ultrasound (for Subjects with an Intact Uterus Only)

A transvaginal ultrasound (TVU) will be conducted to assess the uterus and adnexa. Images obtained will also be used to determine endometrial thickness at the central ultrasound laboratory. Date of the TVU will be entered in the eCRF. The TVU must be performed by a trained study staff member and images must be sent to a central reader. The results of the TVU at Visit 1 (Screening), including centrally-determined endometrial

thickness, will be used to assess eligibility. The subject should not be randomized until the centrally read TVU result indicates the endometrial thickness (double-layer) is <4 mm.

If at Screening, the locally read endometrial thickness is evidently, according to the Investigators judgment, more than 4 mm, the subject would not be eligible for the study and the images from the TVU should not be sent to the central ultrasound laboratory.

At 12 weeks (Visit 5), the TVU will be performed and the endometrial thickness (double-layer) will be determined by a central reader following the same procedure. If the subject leaves the study before Week 12, the TVU should be performed as part of the early termination visit.

Any symptomatic and/or large fibroids (estimated size >3 cm) or uterine polyps observed in the TVU at Screening (Visit 1) will exclude the subject from the study. Subjects with endometrial polyps identified during the study period will be discontinued, endometrial polyps should be reported as an AE, and the AE should be captured as the reason for discontinuation.

Detailed procedures will be specified in a separate document. Details about the central ultrasound laboratory are provided in Section 10.1.

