7.6.5 Biopsy for Endometrial Histology (for Subjects with Intact Uterus Only)

The endometrial biopsy must be obtained after the TVU is performed. Use of oral pain medication is allowed before the biopsy. Local anesthesia will be used if considered necessary by the Investigator. The use of any concomitant medication must be recorded in the eCRF. Endometrial biopsy samples will be taken by the Investigator using a suction curette (Pipelle® or equivalent, aspiration technique). All endometrial samples will be shipped to the central pathology laboratory for preparation of slides.

The endometrial biopsy performed at Visit 1 will be used to evaluate the subject's eligibility for the study and to establish a baseline reading. Subjects with normal or atrophic endometrial histology are eligible to be randomized. Subjects with an insufficient biopsy sample after a valid attempt will be eligible for the study, if the endometrial thickness is <4 mm in the centrally-read TVU. If an endometrial sample cannot be obtained due to cervical stenosis (ie, cervical os cannot be penetrated), the subject is not eligible for the study.

All endometrial histological samples (slides) will be analyzed by concurrent readings by three independent pathologists. Each pathologist will be blinded to the treatment group and to the readings of the other pathologists. The concurrence of two of the three pathologists will be the final diagnosis. If there is no agreement among the three pathologists, the most severe pathologic diagnosis would be used as the final diagnosis. All pathologists will be blinded both to the study treatment and to each other's readings of the histology slides.

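### The Visit 1 list in Protocol 8.1 puts the endometrial biopsy before the site-read ECG, against Section 8's own ordering rule

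*Protocol*

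**What the plan says.** Protocol Section 8 sets a rule for the Screening and Randomization visits: "procedures that may exclude a subject immediately are to be conducted earlier". It gives the reason: "to ensure subjects that will not qualify do not undergo the most invasive/uncomfortable procedures". Section 7.5.11.2 makes the order operative for sites: "At all visits the sequence of procedures should follow Section 8".

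The Visit 1 list in 8.1 has 21 items. The TVU is item 16 and the endometrial biopsy item 17. Item 18 is "Obtain 12-lead ECG (performed in a supine position after ≥ 5 minutes".

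Section 7.6.9 gives the reading of the ECG to the investigator or a designee, and no central reader is named. A clinically significant ECG abnormality is Exclusion 22, listed under Visit 1 in Section 4.3. Section 7.6.9 also sends such a finding to the sponsor's medical monitor for discussion.

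The biopsy applies only to women with a uterus: "Endometrial biopsy samples will be taken by the Investigator using a suction curette". The one ordering condition placed on it is in 7.6.5: "The endometrial biopsy must be obtained after the TVU is performed".

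**The concern.** The list appears to break the rule that introduces it. The ECG is non-invasive, its result is available at the site, and it can make a woman ineligible. The biopsy is plausibly the most invasive item at the visit; 7.6.5 provides for oral pain medication and, if needed, local anesthesia. A site that takes the lines in sequence does the biopsy first and can then find that the woman was never eligible.

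What is at stake is an avoidable suction-curette biopsy in a woman who gains nothing from it. This is a matter of participant burden at screening, not of inference.

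**Working it through.** The protocol gives no figure to reproduce here, so the check is a comparison of the list with the rule.

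1. **Position in the list.** Counting the lines of 8.1: consent 1, subject ID 2, urine 3, demographics 4, medical history 5, prior therapy 6, eligibility review 7, VVA symptoms 8, vital signs 9, physical examination 10, breast examination 11, gynecological examination 12, vaginal pH 13, smear 14, PAP 15, TVU 16, biopsy 17, ECG 18, blood samples 19, AEs 20, mammogram 21.

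2. **What comes before the biopsy.** Items that give the site information tied to a numbered criterion are placed ahead of it: medical history and prior therapy (5, 6), VVA symptoms (8), vital signs with height and weight (9), the three examinations (10 to 12), pH (13) and the local TVU reading (16). The TVU shows the rule at work. If the local reading is clearly above the limit, then under 7.6.4 "the subject would not be eligible for the study and the images from the TVU should not be sent to the central ultrasound laboratory".

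3. **What comes after it.** Blood goes to a central laboratory (7.6.10.2), so it cannot exclude at the visit. AE assessment is not an eligibility test. The mammogram may be ordered rather than done at the visit. That leaves the ECG as the item read at the site and tied to a criterion.

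4. **Is there a reason for the order?** The only stated constraint is TVU before biopsy. Either reordering keeps it:
   - Now: TVU 16, biopsy 17, ECG 18.
   - Swap: TVU 16, ECG 17, biopsy 18.
   - ECG just before TVU: ECG 16, TVU 17, biopsy 18.

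5. **Vaginal infection.** If an infection is found at the gynecological examination (item 12), 7.5.11.2 item 1 postpones the remaining assessments. With the ECG at 16 or 17 it is still postponed, as now. For the situations in its items 2 and 3, item 4 says "The TVU, endometrial biopsy, and ECG do not need to be repeated even if they were assessed prior to the discovery of the infection". So neither placement creates repeat ECGs.

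6. **Size.** Avoidable biopsies = N × p, where N is the number of women with a uterus who reach the biopsy step and p is the share of them excluded on ECG. The documents give neither N nor p. As a unit conversion only, N = 100 and p = 1% gives 100 × 0.01 = 1. Among randomised women the number is 0: each one with a uterus had to have the screening biopsy attempted for Inclusion 8, whatever the order.

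**The case against.** The strongest reply is that Section 8 already resolves this. It describes its lists as arranged for convenience and then states the rule. An instruction to follow Section 8 includes the rule, so a site may do the ECG first. Section 8.1 also does not say that everything happens on one day. This stands in part: the protocol does not forbid the better order, and a reader who inferred that sites are required to biopsy first would be going too far. It does not remove the inconsistency, because the itemised sequence that sites are told to follow points the other way.

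A second reply is that the ECG may not exclude on the spot, since 7.6.9 calls for a discussion with the medical monitor. That is right about timing, and exclusion is not always immediate. But the rule covers procedures that may exclude, and Section 4.3 makes a woman who meets Exclusion 22 ineligible without exception. A pending discussion is a reason to wait with the biopsy.

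A third reply concerns how far to move the ECG. A reader might infer that it belongs right after vital signs. The conflict does not need that. It would give an ECG to women who then fail at the physical examination through the TVU. It would also put the ECG before an infection found at the gynecological examination, a case that 7.5.11.2 item 4 does not clearly cover.

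**Conclusion.** The inconsistency is real and minor. The list order can be checked directly. The conclusion rests on reading the 8.1 list as a sequence, which 7.5.11.2 supports, and on the site having the ECG result at the visit, which 7.6.9 supports.

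The only women affected are those with a uterus who reach the biopsy and are then excluded on ECG. The number is probably small. It cannot be derived, because the documents give no number screened, no share of screened women with a uterus and no ECG exclusion rate. Women who fail only on results that arrive later (maturation index, PAP, central TVU reading, central laboratory tests) would not be helped.

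A reader might infer a large number from the 60% cap on women without a uterus, which implies at least 0.40 × 600 = 240 randomised women with one. The documents do not support that use, since all of those women needed the biopsy. Nor is there support for any effect on efficacy or safety results.

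**What to change.** In 8.1, move the ECG line ahead of the biopsy, either by swapping items 17 and 18 or by placing it just before the TVU, and keep the biopsy after the TVU. The swap adds no ECG for women who fail on the local TVU reading. The earlier placement also spares ECG failures the TVU. Add that the biopsy is not done when the ECG shows a clinically significant abnormality unless the medical monitor discussion has cleared the woman.

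As a minor alignment, limit the discussion in 7.6.9 to whether the finding is clinically significant. At present that section leaves enrolment open for a woman whom Exclusion 22 rules out.

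No procedure is added. The costs are:
- An occasional return visit for the biopsy when the monitor's answer is pending. It must fit in the 28-day screening period and leave time for the pathology result before Visit 2.
- Written IRB approval of the wording change (Section 10.10) and notice to sites. The change does not justify an amendment of its own and can be bundled with another.
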